Study Identification

Unique Protocol ID: IFCI-04/10/2015

Brief Title: Autologous Dendritic Cell Vaccine for Treatment of Patients with Chronic HCV-Infection

Official Title: Safety/Efficacy of Vaccination with Autologous Dendritic Cells Pulsed with Recombinant HCV-Antigens (Core and NS3) for Treatment of Patients with Chronic HCV-Infection

The protocol was approved by the Ethics Committee of the Institute of Fundamental and Clinical Immunology (approval number: no 88, 04/10/2015)

Study Description

Purpose/Brief Summary:

Clearance of HCV infection requires earlyand multi-specific HLA class I restricted CD8+ T cell and class II restricted CD4+ T cell responses to both structural (Core) and non-structural HCV proteins (NS3, NS4A, NS5A, NS5B). Dendritic cells (DCs) are professional antigenpresenting cells that link innate and adaptive immune responses, and play a major role in priming, initiating, and sustaining strong anti-HCV T cell immune responses.

The general objective of this study is to evaluate safety, feasibility and clinical efficacy of therapeutic vaccinationin genotype 1 HCV patients using autologous DCs pulsed with recombinant HCV-antigens (Core and NS3). Expected effects: DC vaccination induces Core/NS3-specific immune response and reduces viral load in patients with chronic HCV-infection.

Condition	Intervention	Phase
Hepatitis C, Chronic	Biological: Autologous monocyte-derived dendritic cells,	Phase 1
	generated in the presence of IFN- α /GM-CSF and pulsed with recombinant HCV Core (1-120) and NS3 (1192-1457)	Phase 2
	proteins.	

Detailed Description:

Hepatitis C virus (HCV) has chronically infected an estimated 170 million people worldwide. People infected with HCV are at risk for developing chronic liver diseases, such as liver cirrhosis and primary hepatocellular carcinoma. It has been estimated that HCV accounts for 27% of cirrhosis and 25% of hepatocellular carcinoma worldwide. Therapy for chronically HCV-infected patients has involved a pegylated interferon-alpha and ribavirin (pegIFN/RBV) and is still the only FDA-approved therapeutic combination. However, this therapy is expensive, non-specific, toxic, and only effective in about 50% of genotype-1 HCV patients.

An early immune response, represented by the activation of NK cells, the development of vigorous anti-HCV CD4+ and CD8+ T-cell responses, and the appearance of HCV-specific antibodies, is mounted by the host during acute HCV infection and leads to clearance of the virus. However, in the vast majority (\approx 85%) of infected individuals HCV causes a persistent infection. The mechanisms of HCV persistence remain elusive and are largely related to inefficient clearance of the virus by the host immune system.

Although HCV genome is very variable with hundreds of serotypes and six genotypes, several structural (Core) and nonstructural proteins (NS3, NS4A, NS5A, NS5B) are highly conserved among genotypes and subtypes. It is apparent that clearance of hepatitis C infection requires early and multi-specific HLA class I restricted CD8+ T cell and class II restricted CD4+ T cell responses to both structural and non-structural HCV proteins.

DCs are professional antigen-presenting cells that link innate and adaptive immune responses. DCs play a major role in priming, initiating, and sustaining strong T cell responses against pathogen-derived antigens. Therefore DC-based therapy represents a promising immunotherapeutic approach in terms of their propensity to establish anti-HCV adaptive immune responses.

This trial is a prospective, non-blinded, interventional study to determine safety, feasibility and clinical efficacy of therapeutic vaccination in genotype 1 HCV patients using autologous DCs pulsed with recombinant HCV-antigens (Core and NS3). Our previous work has shown that the short-term loading of DCs with recombinant HCV proteins Core (1-120) and NS3 (1192-1457) have no any marked inhibitory effect on maturation and functions of DCs [Oleynik E.A., et al. 2016].

In experimental group thirty patients with chronic hepatitis C (genotype 1) will be vaccinated via intracutaneous injection of monocyte-derived DCs, generated in the presence of IFN- α /GM-CSF and pulsed with recombinant HCV Core (1-120) and NS3 (1192-1457) proteins. The vaccination protocol will includes initiating (one injection per week, no 4) and maintaining (one injection per month, no 6) courses with subsequent 6-month of follow up.

The safety will be determined by the evaluation of the number of participants with the adverse events. Liver safety will be assessed by blood analysis and Ultrasound. Patients will be monitored in a 2 months (after completing of initiating course), 7 months (after completing of maintaining course) and 13 months (in a 6 months post-vaccination follow-up).

Conditions

Conditions: Hepatitis C, Chronic; Liver Diseases; Hepatitis, Viral, Human; Hepatitis, Chronic; Virus Diseases.

Keywords: Dendritic Cells; DC-based Vaccines; Chronic HCV Infection; Antigen-Specific T cell response; Recombinant HCV-Core antigen; Recombinant HCV-NS3 antigen.

Study Design

Study Type: Interventional Primary Purpose: Treatment Study Phase: Phase 1/Phase 2 Intervention Model: Single Group Assignment Number of Arms: 1 Masking: No masking Enrollment: 30

Arms and Interventions

Arms	Assigned Interventions
Experimental: Autologous DC-vaccines	Biological/Vaccine: Autologous DC-vaccines
Thirty patients with chronic hepatitis C (genotype 1) will receive the initiating and maintaining courses of autologous monocyte-derived dendritic cells, generated in the presence of IFN- α /GM-CSF and pulsed with recombinant HCV Core (1-120) and NS3 (1192-1457) proteins.	Patients will be vaccinated via intracutaneous injection of autologous DCs (5×10^6) combined with adjuvant subcutaneous injection of recombinant hIL-2 (250 000 IU). Initiating course: one vaccination per week, during 1 month. Maintaining course: one vaccination per month, during 6 month. Patients will be monitored in a 2 months (after completing of initiating course), 7 months (after

completing of maintaining course) and 13 months (in a 6 months post-vaccination follow-up).

Outcome Measures

Primary Outcome Measure:

1. Number of Participants with Severe Adverse Reactions and/or With Abnormal Clinical Laboratory Values That Are Related to Treatment

[Time Frame: From enrollment and up to 13 months]

Frequency of severe adverse reactions will be evaluated from enrollment and up to 13 months. Liver safety by blood analysis (ALT, AST, GGT, Total and conjugated bilirubin, platelets, ESR, etc) and Ultrasound will be assessed from enrollment and up to 13 months (= baseline, 2, 7 and 13 months after 1-st vaccination).

Secondary Outcome Measure:

2. Number of Participants with Virological Response According to HCV RNA Viral Load [Time Frame: Baseline, 2, 7 and 13 month after 1-st vaccination]

Virological response in patients receiving DC-vaccinations is defined as change from baseline in HCV RNA viral load by at least 1 log at 2, 7 and 13 month after 1-st vaccination. Plasma level of HCV RNA will be measured by Real-Time Reverse Transcription-Polymerase Chain Reaction (RT-PCR)

3. Number of Participants Who Have Developed or Increased Anti-Viral Immune Response According to T-cell proliferation

[Time Frame: Baseline, 2, 7, and 13 months after 1-st vaccination]

Change from baseline in T-cell proliferative response to HCV Core and NS3 proteins at 2, 7 and 13 month after 1-st vaccination. T-cell proliferation will be evaluated using radiometry based on 3H-thymidine incorporation.

4. Number of Participants Who Have Developed or Increased Anti-Viral Immune Response According to $IFN-\gamma$ production

[Time Frame: Baseline, 2, 7, and 13 months after 1-st vaccination]

Change from baseline in T-cell IFN- γ -producing response to HCV Core and NS3 proteins at 2, 7 and 13 month after 1-st vaccination. Production of IFN- γ will be measured by ELISA kit

Eligibility

Minimum Age: 18 Years Maximum Age: 65 Years Sex: All Accepts Healthy Volunteers: No

Criteria:

Inclusion Criteria:

- Age 18 to 65 Years (Adult)
- Chronic hepatitis C (genotype 1b)
- HCV-positive patients
- Plasma HCV RNA level $\geq 10^4$ IU/ml
- Liver fibrosis (METAVIR Score 0-III)

- Patients must be able totolerate all study procedures
- Patients must be willing to voluntarily give written Informed Consent to participate in the study before any procedures are performed
- Patients must be willing to be available for all baseline, treatment and follow-up examinations required by protocol

Exclusion Criteria:

- Co-infection with hepatitis B, A, D, E, cytomegalovirus or Epstein-Barr virus
- Liver cirrhosis (METAVIR Score IV)
- The high degree of hepatitis activity (ALT and/or $AST \ge 10$ ULN)
- Received any vaccine within a month prior to study entry
- A history of diabetes
- Psychiatric disorders
- Renal dysfunctions
- Hemodynamic or respiratory instability
- HIV or uncontrolled bacterial, fungal, or viral infections
- Autoimmune diseases
- Pregnancy
- Malignancy
- Participation in other clinical trials

Contacts/Locations

Central Contact: [name] [contact] Email: [contact]

Central Contact Backup: [name] [contact] Email: [contact]

Study Chair: [name], PhD

Study Principal Investigator: [name], PhD

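### The laboratory part of the primary safety count admits only abnormalities judged related to treatment, so in an unmasked one-arm trial a real liver-test worsening can be left out as disease

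*Protocol*

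**What the plan says.** In the protocol, Outcome Measures, the single primary outcome is the "Number of Participants with Severe Adverse Reactions and/or With Abnormal Clinical Laboratory Values That Are Related to Treatment", with "Time Frame: From enrollment and up to 13 months". The supporting text says "Liver safety by blood analysis (ALT, AST, GGT, Total and conjugated bilirubin, platelets, ESR, etc) and Ultrasound will be assessed" and gives the assessment times as "baseline, 2, 7 and 13 months after 1-st vaccination". A pre-vaccination value is therefore collected for each participant, but no rule links later values to it. Neither document defines an abnormal value, or says who judges relatedness and by what criteria.

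Study Design gives "Number of Arms: 1 Masking: No masking", with 30 participants.

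Under Eligibility, the exclusion headed "The high degree of hepatitis activity (ALT and/or" AST applies only from 10 times the upper limit of normal. No limit is set for GGT or bilirubin, and the inclusion criteria admit "Liver fibrosis (METAVIR Score 0-III").

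The virological secondary outcome is built differently: response "is defined as change from baseline in HCV RNA viral load by at least 1 log". The two T-cell outcomes are also expressed as change from baseline, though without a threshold.

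The SAP lists medians with interquartile ranges, Mann–Whitney and Wilcoxon tests, and Spearman correlation. It does not mention the primary participant count.

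**The concern.** Relatedness is hard to judge in this trial. The patients have chronic hepatitis C, so their liver tests can be abnormal and can change without any treatment. The vaccine is intended to strengthen T-cell responses to two HCV antigens in those same patients, so a rise in liver tests could come from the vaccine or from the disease. No control arm shows how often such rises occur without the vaccine, and whoever judges relatedness knows that every participant was vaccinated.

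Under the stated rule, that judgement decides whether a worsened value enters the laboratory part of the primary result. A laboratory count of zero could mean that nobody worsened, or that some did and were attributed to hepatitis C. A reader of the result could not tell which. This matters because it is the trial's only primary outcome and its subject is safety.

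**Working it through.** **No figure to reproduce.** The protocol gives 30 participants without an expected event rate, precision or power statement. The check is a reading of the rule, plus a small illustration.

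**Inputs from the documents.** n = 30, one arm, no masking (Study Design). Laboratory tests at baseline and months 2, 7 and 13 (Outcome Measures). Transaminases up to, but not including, 10 times the upper limit admitted (Eligibility).

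**Input assumed.** The number of participants whose laboratory values truly worsen, w. The documents give no rate, so w = 0, 1 and 3 are used for illustration.

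**The rule.** Let r be the number of the w worsened participants judged related, and set unchanged abnormalities aside.

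- Laboratory count as written = r, where 0 ≤ r ≤ w.
- Count of worsening from own baseline, regardless of attribution = w.
- Shift for each participant judged disease-related = 1/30 = 3.3 percentage points.

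**Exact (Clopper–Pearson) 95% limits for x of 30.** Lower = 2.5% quantile of Beta(x, 31 − x), or 0 when x = 0. Upper = 97.5% quantile of Beta(x + 1, 30 − x). For x = 0 the upper limit reduces to 1 − 0.025^(1/30) = 0.116.

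| Count | Proportion | Exact 95% CI |
|---|---|---|
| 0/30 | 0% | 0% to 11.6% |
| 1/30 | 3.3% | 0.1% to 17.2% |
| 3/30 | 10.0% | 2.1% to 26.5% |

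**Result.**

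- w = 0: both counts are 0/30 and attribution changes nothing.
- w = 1: the count as written is 0 or 1.
- w = 3: the count as written is anything from 0 to 3. At the extreme the estimate falls by 3/30 = 10 percentage points, and the upper confidence limit falls from 26.5% to 11.6%, a difference of 14.9 points.

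The confidence interval does not reveal this loss, because it covers sampling error and not misattribution. The figures concern the laboratory component. A participant who also has a severe adverse reaction would still be in the composite.

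**Can the SAP's paired test fill the gap?** A Wilcoxon test for dependent samples could compare laboratory values with baseline at group level. The SAP does not assign it to laboratory safety. It is also not designed to detect worsening in a few individuals, and it does not decide which participants count.

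**The case against.** The strongest reply is that the relatedness condition already does useful work. An abnormality present before vaccination and unchanged afterwards cannot sensibly be attributed to the vaccine, so the condition implies a before/after comparison. This stands. A reader might infer from the lenient entry limits that the count will fill up with pre-existing abnormalities. The documents do not support that as a likely outcome, because it would need an assessor to attribute to the vaccine findings that predate it.

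A reader might also infer, from the time frame starting at enrollment, that baseline values are themselves counted. That is not supported either. Baseline is listed as an assessment time, most naturally serves as the reference visit, and cannot meet the relatedness condition. Collecting severe reactions from enrollment is defensible in its own right.

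Three further replies stand in part:

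- The undefined terms, abnormal and related, are by themselves missing detail. True, but the choice to count only attributed abnormalities would remain a problem after both were defined.
- The Detailed Description speaks of the number of participants with adverse events, without a relatedness condition, so an excluded case might be reported there. It might, but neither document commits to counting laboratory worsening there.
- An attribution-free count has its own weaknesses: it moves with the chosen threshold and takes in natural fluctuation. That is why the related subset should be shown beside it.

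**Conclusion.** The point holds, as a low-cost improvement to how the primary outcome is counted. The stated rule lets an unmasked, uncontrolled attribution judgement remove a real liver-test worsening from the primary safety count. The error to guard against is mainly under-counting; over-counting of unchanged abnormalities is possible but less likely.

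The size is 3.3 percentage points per participant moved. With an assumed three true worsenings, the reported laboratory result could lie anywhere between 3/30 and 0/30. The number of worsenings is an assumption, and so is the extreme case in which all are judged disease-related. The documents give no rates and do not show that misattribution will occur. The data needed to avoid the problem are already scheduled: the gap lies in the outcome rule, not in data collection.

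**What to change.** From the scheduled baseline and month 2, 7 and 13 tests, report the number of participants whose laboratory values worsen from their own pre-vaccination baseline, regardless of attribution. Use one named grading scale, with the scale and the worsening threshold pre-specified by the sponsor. Apply this count to values after the first vaccination, and keep the collection of severe adverse reactions from enrollment as it is.

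Beside it, show the subset judged related, with the method of judgement stated, and a baseline-to-worst shift table. Give each count an exact 95% CI out of all vaccinated participants (30 planned).

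Two secondary clarifications would help: say whether and how ultrasound findings enter the count, and reconcile the primary outcome with the adverse-event sentence in the Detailed Description.

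The cost is revised outcome wording, a named scale, a stated relatedness method and one table, with no extra visits or tests. The downside is that, without a control arm, the attribution-free count will include natural fluctuation of chronic hepatitis and will depend on the threshold chosen.

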Study Identification

ClinicalTrials.gov ID: NCT03119025

Unique Protocol ID: IFCI-04/10/2015

Brief Title: Autologous Dendritic Cell Vaccine for Treatment of Patients with Chronic HCV-Infection

Official Title: Safety/Efficacy of Vaccination with Autologous Dendritic Cells Pulsed with Recombinant HCV-Antigens (Core and NS3) for Treatment of Patients with Chronic HCV-Infection

The protocol was approved by the Ethics Committee of the Institute of Fundamental and Clinical Immunology (approval number: no 88, 04/10/2015)

April 10, 2015

Statistical Analysis Plan

Data will be analyzed using Statistica 9.0 software. The results of statistical analysis will be presented as median and interquartile range. The Mann–Whitney test (for independent samples; p_U) and Wilcoxon test (for dependent samples; p_W) will be applied, and differences with p less than 0.05 will be considered statistically significant. Correlation analysis will be conducted by Spearman's rank-order correlation (R_S).

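### The clinical-event part of the primary safety outcome is limited to severe reactions, while the protocol's description bases safety on all adverse events, and no other outcome or SAP analysis counts the rest

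*Protocol*

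**What the plan says.** The protocol describes the safety measure in two places.

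- **Detailed Description:** "The safety will be determined by the evaluation of the number of participants with the adverse events". No severity or causality condition is attached. The next sentence adds liver safety by blood tests and ultrasound.
- **Outcome Measures, primary outcome:** "Number of Participants with Severe Adverse Reactions and/or With Abnormal Clinical Laboratory Values That Are Related to Treatment". The detail beneath it names only severe reactions for clinical events: "Frequency of severe adverse reactions will be evaluated from enrollment and up to 13 months". It then gives the liver component: "Liver safety by blood analysis (ALT, AST, GGT, Total and conjugated bilirubin, platelets, ESR, etc) and Ultrasound will be assessed", at baseline and at 2, 7 and 13 months after the first vaccination.

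The three secondary outcomes are virological response, T-cell proliferation and IFN-γ production. None concerns adverse events.

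The design is "Intervention Model: Single Group Assignment Number of Arms: 1 Masking: No masking Enrollment: 30". The schedule is four weekly and six monthly injections, ten in all, each combined with subcutaneous IL-2.

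The SAP states that "The results of statistical analysis will be presented as median and interquartile range", names the Mann–Whitney, Wilcoxon and Spearman methods, and sets a 0.05 threshold. It mentions neither adverse events nor any method for participant counts. Neither document gives a severity scale, a method for judging causality, or a threshold for an abnormal laboratory value.

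**The concern.** Safety is the first-named aim of this Phase 1/2 trial and its primary outcome. A participant with moderate fever or local inflammation after several of the ten injections is a safety case under the description. Under the clinical-event part of the primary outcome the same participant is not counted. A severe event judged unrelated to vaccination is also left out if the relatedness condition covers reactions as well as laboratory values.

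If the team reports outcome 1 as written and the SAP as written, the tolerability of the course goes undescribed. A finding of no severe reactions could then be taken as a general statement about safety. The trial is unmasked and has no comparator, so nothing in the design offers a check on a decision that an event was not severe or not related. A tabulation that ignores relatedness does not depend on that decision.

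**Working it through.** **1. What each statement counts**

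| Event in a participant | Detailed Description | Primary outcome |
|---|---|---|
| Severe reaction, related | counted | counted |
| Severe event, judged unrelated | counted | not counted if the relatedness condition covers both parts; unclear otherwise |
| Mild or moderate clinical event, related or not | counted | not counted |
| Related abnormal laboratory value, any severity | not stated separately; liver tests are assessed | counted |

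The two statements part company on the second and third rows. No secondary outcome and no SAP analysis covers those rows.

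**2. Inputs for the size**

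The protocol gives n = 30 in one arm (Study Design) and follow-up to 13 months (Outcome Measures). The documents give no event rate, safety threshold or sample-size derivation, so there is no planned figure to reproduce. All rates below are assumptions. Participants are treated as independent with a common rate.

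**3. Chance that the severe-reaction count is zero**

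P(0 of 30) = (1 − p)^30, where p is the true rate of counted severe reactions.

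| p | P(0 of 30) |
|---|---|
| 1% | 0.99^30 = 74% |
| 2% | 0.98^30 = 55% |
| 5% | 0.95^30 = 21% |
| 10% | 0.90^30 = 4% |

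The rate of mild, moderate or unattributed events does not enter the formula.

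**4. What 0/30 would show**

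The exact upper limit is 1 − a^(1/30). Two-sided 95%: 1 − 0.025^(1/30) = 11.6%. One-sided 95%: 1 − 0.05^(1/30) = 9.5%. Both apply only to the severe reactions that are counted.

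**5. The two counts side by side**

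Suppose 80% of participants have some adverse event and 5% of those have a severe related one. The expected number with any event is 30 × 0.80 = 24. The expected number with a severe related event is 24 × 0.05 = 1.2. The chance that the latter count is zero is (1 − 0.80 × 0.05)^30 = 0.96^30 = 29%. With an any-event rate of 50% and the same 5% share, the expected numbers are 15 and 0.75, and the chance of zero is 0.975^30 = 47%.

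**6. The whole composite**

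With no severe reactions at all, the primary count is zero only if no participant has a related laboratory abnormality. For a related-abnormality rate r, P(0) = (1 − r)^30: 21% at r = 5%, 4% at 10% and 0.1% at 20%. The laboratory part can thus lift the composite above zero without any severe reaction.

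**The case against.** Several points on the other side stand.

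- **The outcome is a composite.** A reader might infer that it counts only severe, treatment-related reactions and so could show no harm at all whatever the true rate of other events. The documents do not support that. Abnormal laboratory values count without a severity limit, and step 6 shows that modest rates of related abnormality make a zero composite unlikely. Independence from other clinical events is a property of the severe-reaction component alone.
- **The wider count is promised.** A reader might infer that outcome 1 is the only safety result that will be reported. The Detailed Description commits to the number of participants with adverse events, and a general statement followed by a narrower primary outcome need not be a contradiction. What can be said is that outcome 1 is the only listed safety outcome and that the SAP does not carry out the wider promise.
- **An outcome definition is not a recording rule.** Nothing says that non-severe or unrelated events go unrecorded or are discarded.
- **The relatedness condition is ambiguous.** It may qualify both parts or only the laboratory values, although the word reactions usually implies relatedness. Neither document says who grades severity or judges cause.
- **A focused primary outcome is legitimate.** A sponsor may choose severe reactions and laboratory abnormalities as its headline.

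None of this closes the gap. The listed tests (liver enzymes, bilirubin, platelets, ESR) and ultrasound do not count fever or injection-site reactions, and they are scheduled at four time points rather than after each injection. The laboratory part also depends on attribution, with no threshold for abnormal, in patients who may enter with ALT and AST anywhere below 10 ULN.

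**Conclusion.** The concern holds in a limited form. The two safety statements differ for clinical events: one is restricted to severe reactions and the other is not. Mild, moderate and unattributed clinical events fall outside every listed outcome and every SAP analysis.

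The severe-reaction component can be 0/30 regardless of how common those events are, and that result would exclude only severe-reaction rates above 11.6% (exact, two-sided 95%). It would say nothing about tolerability. The composite may still be above zero through laboratory abnormalities.

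The 11.6% limit assumes that all 30 participants are enrolled and evaluable. The other probabilities rest on assumed rates and illustrate the mechanism; they do not predict this trial's results. The point is a worthwhile, low-cost improvement to the outcome wording and safety reporting. It is not evidence that harm would be concealed.

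**What to change.** 1. Reconcile the Detailed Description with the primary outcome so that the protocol states which safety counts will be reported.
2. Record every adverse event from enrollment to 13 months with grade, seriousness and relatedness, and name the grading scale and the causality method.
3. Add a safety table to the SAP: number of participants with any adverse event, any serious adverse event and any severe adverse event, each regardless of relatedness, with exact confidence intervals.
4. Keep the existing primary count as defined (severe reactions and/or related abnormal laboratory values). Show its two components separately, state whether the relatedness condition applies to both, and state the threshold for an abnormal value.

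The cost is one extra table, fuller event recording and a short wording change. The safety summary may look less favourable. Treatment, visits and sample size are unchanged.

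### Does the virological response definition leave the responder count open, by not fixing a visit rule or a direction of change?

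*Protocol*

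**What the plan says.** The protocol's Outcome Measures section titles secondary outcome 2 "Number of Participants with Virological Response According to HCV RNA Viral Load" and gives its schedule as "Time Frame: Baseline, 2, 7 and 13 month after 1-st vaccination". Response is "defined as change from baseline in HCV RNA viral load by at least 1 log at 2, 7 and 13 month after 1-st vaccination". The Purpose/Brief Summary states the expected effect: "DC vaccination induces Core/NS3-specific immune response and reduces viral load in patients with chronic HCV-infection". The Study Design entry reads "Number of Arms: 1 Masking: No masking Enrollment: 30", so there is no control group. One inclusion criterion is "Plasma HCV RNA level $\geq 10^4$ IU/ml".

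The SAP is a single paragraph that does not mention virological response. It says "The results of statistical analysis will be presented as median and interquartile range", names the Mann–Whitney test for independent samples and the Wilcoxon test for dependent samples, and adds that "differences with p less than 0.05 will be considered statistically significant".

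**The concern.** The outcome is a number of participants, so each person must be classed as a responder or not. The definition joins three visits with the word 'and', and three counting rules fit that grammar: the threshold is met at any visit, at all three, or judged at each visit separately. Neither document picks one. The SAP's only stated form of presentation, a median with quartiles, does not produce a responder count.

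The visits also mean different things. Month 2 follows the initiating course, month 7 follows the maintaining course, and month 13 comes six months after vaccination ends. A brief early fall and a lasting one are different findings.

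The word 'change' carries no sign, so a rise of 1 log would qualify on a literal reading, and the base of the logarithm is not given.

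Clinical efficacy is a stated objective, and this is the only listed outcome that measures viral load. In an unblinded single-arm trial no control count would expose an inflated rate. If the counting rule were chosen after the data were seen, the reported number out of 30 could move a good deal without breaching the written plan.

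**Working it through.** **The texts side by side**

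1. *Visits.* The time frame for outcome 2 lists baseline and months 2, 7 and 13. Secondary outcomes 3 and 4 (T-cell proliferation and IFN-γ production) have the same title form, a number of participants, and describe a change from baseline at the same three visits. There the phrase most naturally means a change assessed at each visit. Nothing suggests that outcome 2 uses the same construction differently.
2. *Test.* The Wilcoxon test for dependent samples compares two paired measurements. That suits baseline against each later visit; it suits a composite over visits less well.
3. *Title.* A number of participants can be tabulated at each time point, so the title does not demand one overall figure.
4. *Direction.* The summary expects viral load to fall, and the quantity defined is a response. Both exclude a rise.
5. *Log base.* The entry criterion is written as a power of ten, which points to log10.

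**Size, for illustration**

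The plan gives no response rate, variability or sample-size derivation, so there is no figure to reproduce.

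- From the documents: N = 30, three post-baseline visits, threshold 1 log.
- Assumed: log10 scale, normal errors, within-patient SD s = 0.3, 0.4 or 0.5, and one baseline measurement shared by all three comparisons.

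Model: change at visit j = μ + b − e0 + ej. The measurement errors e0 and ej have SD s. The patient's own deviation b has SD τ. A response is a change of −1 or lower.

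- One visit: Φ((−1 − μ)/√(2s² + τ²)).
- Any visit and all three visits: let p be the response probability at a visit given the shared part μ + b − e0. Then any = E[1 − (1 − p)³] and all = E[p³], integrated numerically.

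Worked one-visit values at s = 0.3 and μ = −0.5:

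- τ = 0: √0.18 = 0.424; −0.5/0.424 = −1.18; Φ = 0.119; × 30 = 3.6.
- τ = 0.5: √(0.18 + 0.25) = 0.656; −0.5/0.656 = −0.76; Φ = 0.223; × 30 = 6.7.

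Expected responders out of 30, decrease only, for s = 0.3 / 0.4 / 0.5:

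| Assumed truth | One visit | Any visit | All three | Any ÷ one |
|---|---|---|---|---|
| No effect | 0.3 / 1.2 / 2.4 | 0.7 / 2.8 / 5.3 | 0.01 / 0.1 / 0.3 | 2.7 / 2.4 / 2.3 |
| Decline of 0.5 in every patient | 3.6 / 5.7 / 7.2 | 7.6 / 11.1 / 13.4 | 0.6 / 1.4 / 2.0 | 2.1 / 2.0 / 1.9 |
| Mean decline 0.5, SD between patients 0.5 | 6.7 / 7.6 / 8.5 | 10.4 / 12.3 / 13.8 | 3.4 / 3.5 / 3.7 | 1.6 / 1.6 / 1.6 |

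Ratios are taken before rounding. Counting rises as well as falls about doubles the no-effect row and adds less than 20% to any count in the other two rows. With no effect and s = 0.2, every rate is 0.12% or lower, even if both directions count.

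**The case for a change.** The case for a change is that no sentence in either document states the counting rule, and that inferring intent from parallel wording is weaker than writing it down. Comparing any visit with all three, the same data would give about 7- to 12-fold different counts under a uniform decline and about 3- to 4-fold under a varying one. Even if counts are given per visit, there are three of them, and nothing says which one would support an efficacy statement. The remedy would cost only a sentence or two.

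Part of this stands. The rule is indeed unwritten, and if a report quoted a single responder figure, a reader could not tell from the plan which visit it should come from.

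The rest carries less weight. The large multiples set against each other the two readings with least support in the text; compared with the per-visit reading, the ratio is far smaller. The three visits are fixed in advance, so once all three counts are shown no visit rule is left to choose. Naming one main visit would be good practice, but its absence is not an error in a secondary outcome to which no decision is tied. The SAP's silence on counts applies to every outcome expressed as a number of participants, so it shows nothing particular about this visit rule.

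**Conclusion.** This is loose drafting that analysts will fill sensibly, and no change to the plan follows. The context supports a decrease of at least 1 log10, counted separately at months 2, 7 and 13; writing that out would alter no result an analyst would otherwise produce.

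Departing from that reading to an any-visit count would give about 1.6 to 2.1 times as many responders if a mean decline of 0.5 log10 is assumed, and about 2.3 to 2.7 times if there is no effect, where the counts are small (at most 5.3 of 30). These ratios rest on assumed SDs of 0.3 to 0.5, normal errors and a shared baseline, none of which the documents supply. The conclusion about intent rests on the wording alone and does not depend on them.

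A reader of the results should expect three counts, and should be wary of a single responder figure given without its visit.
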